8.2. Study Design Considerations

8.2.1. Sample Size Assumptions

A total of 330 women (165 women per treatment group) will be recruited into the study and randomly assigned to treatment to ensure that 300 women/newborns (150 women/newborns per treatment group, assuming 10% missing data) have recorded

birth data, which provides 86% statistical power to detect an average difference of 9.5 days between retosiban and atosiban in time to delivery in the proposed adaptive design with futility analysis.

The above sample size calculations are based on a 2-sided testing procedure with a type I error rate of 5% and an approximate 10% dropout rate. Calculations are based on simulations and assumes that the percentage of women enrolled into each of the GA strata $24^{0/7}$ to $25^{6/7}$, $26^{0/7}$ to $27^{6/7}$, $28^{0/7}$ to $30^{6/7}$, and $31^{0/7}$ to $33^{6/7}$ will be 7%, 13%, 27%, and 53% (1:2:4:8 ratio), respectively, and approximately 55% of women in the atosiban treatment group will deliver within the 3 weeks of GA at randomization. The details of the model assumption and simulation are included in a supplemental simulation report.

Statistical Operating Characteristics

Simulations were carried out to determine the statistical properties for inference about the primary hypothesis of the adaptive design with regard to the control of the overall type I error and the statistical power under a wide range of efficacy for retosiban, from no effect (i.e., null hypotheses) to an increase of 9.5 days in time to delivery (i.e., alternative hypothesis) and to greater than expected efficacy. It was shown that the overall type I error rate (2.4%) was maintained at a level well below the 5% for the primary hypothesis. Furthermore, if the true effect of retosiban is small or zero, there is good probability (74%) that the study will be stopped early for lack of efficacy (i.e., futility). If the true effect of retosiban is as expected, the statistical power will be 86%, with a 7% probability that the study will be stopped for lack of efficacy. The details of model assumption and simulation are included in a supplemental simulation report.

Table 7 Operating Characteristics of the Adaptive Design Under the Null and Alternative Hypotheses

Case Hypothesis	Interim Analysis		Final	
	Futility	Failure	Failure	Success
Null (0 day)	74%	24%		2.4%
Alternative (9.5 days)	7%	7%		86%

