2.3. Study Design

Overview of Key Study Design Features	
Design Features:	
 Phase III, randomized, double-blind, double-dummy, multicenter design Subjects are females, aged 18 to 45 years (Sweden) or aged 12 to 45 years (all other countries including UK, Germany, Italy, Israel, South Korea, Belgium, Mexico, Spain and Brazil), with an uncomplicated, singleton pregnancy and intact membranes in preterm labor between 24^{0/7} and 33^{6/7} weeks of gestation.
Dosing:	
 Retosiban treatment will be administered as a 6-mg IV loading dose over 5 minutes, followed by a 6-mg/hour continuous infusion over 48 hours. Atosiban will be given intravenously in 3 successive stages: an initial bolus dose of 6.75 mg using atosiban 6.75 mg/0.9 mL solution for injection, immediately followed by a continuous high dose infusion at 18 mg/hour for 3 hours, then a lower 6 mg/hour infusion for the remainder of the 48-hour treatment period using the atosiban 37.5 mg/5 mL concentrate for solution.
Treatment Assignment:	
 A total of 97 patients were blindly randomly assigned to retosiban or atosiban in a 1:1 ratio. Subjects were stratified by established progesterone treatment (Yes/No) and gestational age at randomization (24^{0/7} to 25^{6/7}, 26^{0/7} to 27^{6/7}, 28^{0/7} to 30^{6/7} and 31^{0/7} to 33^{6/7}). Subjects within each stratum will be randomly assigned in 1:1 ratio to receive either retosiban or atosiban using an IVRS in accordance with the randomization schedule.
Interim Analysis	
 The study was terminated before interim analysis due to feasibility. Details of the interim analysis were written in the IDMC RAP.

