8. SECONDARY AND EXPLORATORY ANALYSES

8.1. Secondary Efficacy Analyses

8.1.1. Overview of Planned Efficacy Analyses

The secondary efficacy analyses will be based on the Maternal and Neonatal ITT Populations.

Table 4 provides an overview of the planned efficacy analyses with further details of data displays presented in Appendix 11: List of Data Displays.

Table 4 Overview of Planned Efficacy Analyses

	Stats Analysis			Summary		Individual	
	T	F	L	T	F	F	L
Key Secondary Endpoints							
Proportion of births prior to 37 ^{0/7} weeks' gestation – ascertain the GA at delivery based on a records review	Y			Y			
Proportion of births at term (37 ^{0/7} to 41 ^{6/7} weeks' gestation) – ascertain the GA at delivery based on a records review	Y			Y			
Length of neonatal hospital stay – duration (in days) of neonatal hospital admission from the medical records	Y			Y			Y
Neonatal composite endpoint	Y			Y			Y
Other Secondary Endpoints							
Individual neonatal composite endpoint				Y			Y
Neonatal composite endpoint without RDS	Y			Y			Y
Neonatal composite endpoint without RDS and mortality	Y			Y			Y
Neonatal admission to a specialized				Y			Y

	Stats Analysis			Summary		Individual	
	T	F	L	T	F	F	L
care unit and length of stay							
Newborn hospital readmission and length of stay				Y			Y
Proportion of births prior to 28 ^{0/7} weeks' gestation	Y			Y			
Proportion of births prior to 32 ^{0/7} weeks' gestation	Y			Y			
Proportion of births prior to 35 ^{0/7} weeks' gestation	Y			Y			
Proportion of births ≤7 days of IP administration	Y			Y			
Proportion of births ≤48 hours of IP administration	Y			Y			
Proportion of births ≤24 hours of IP administration	Y			Y			

NOTES :

- T = Table, F = Figure, L = Listing, Y = Yes display generated.
- Stats Analysis = Represents TFL related to any formal statistical analyses (i.e. modelling) conducted.
- Summary = Represents TF related to any summaries (i.e. descriptive statistics) of the observed raw data.
- Individual = Represents FL related to any displays of individual subject observed raw data.

1. Will be presented in the integrated analysis.

Following review of the data, additional analyses maybe conducted to further support the evaluation and interpretation of the data.

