	
 • For the endpoints of neonatal composite outcome, proportion of births prior to $37^{0/7}$ weeks' gestation, and proportion of births at term ($37^{0/7}$ to $41^{6/7}$ weeks' gestation), a logistic regression model will be used for comparing retosiban with atosiban, with GA at randomization and established progesterone use (yes or no) as covariates. The model will use a logit link function to estimate the log odds of percentage of preterm birth. The model will include terms for treatment group, established progesterone use, and GA at randomization. Additionally, interactions between GA at randomization and treatment and established progesterone use and treatment will also be investigated. • Length of hospital stay will be log-transformed (at base 10) prior to analysis. Log-transformed length of hospital stay will be analyzed using an analysis of covariance adjusting for the covariate of GA at randomization and established progesterone use (yes or no). Additionally, interactions between GA at randomization and treatment and established progesterone use and treatment will also be investigated. Wilcoxon rank sum test will also be performed to compare the two treatments if length of hospital stay is not log normal. • Terms fitted in the model will include: Fixed Categorical: TRT, EP and their interaction term (TRT*EP). Interaction will

Key Secondary Efficacy Statistical Analysis	
Fixed Continuous Covariates:	be included only if the interaction is statistically significant (at 0.1 level of significance). GA and interaction term (TRT*GA). Interaction will be included only if the interaction is statistically significant (at 0.1 level of significance).
Repeated:	None
SAS Code	

 Analysis of Covariance: <pre>ods output lsmeans=means diff=diffs tests3=tests; proc mixed data=xxx; class EP TRT; model log_LoS= TRT EP GA TRT*EP TRT*GA/ddfm=kr s; lsmeans TRT /pdiff cl alpha=0.05; run;</pre> Wilcoxon rand sum test: <pre>proc npar1way data=xxx Wilcoxon; class TRT; var log_LoS; ods output wilcoxontest=wtest; run;</pre> 	
Model Checking & Diagnostics	

 Refer to Appendix 9: Model Checking and Diagnostics for Statistical Analyses. 	
Model Results Presentation	

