
 For binary endpoints, the number and percentage of subjects in each treatment group, the relative risk (RR) and 95% CIs, the odds ratio (OR) of response rates (retosiban versus atosiban) and 95% CIs, and p-value will be presented. The model-adjusted length of stay will be presented for each treatment group. In addition, the treatment difference between retosiban and atosiban and associated 95% CIs and p-values will be presented. Observed values using descriptive statistics for length of stay will be presented for each treatment group. For proportion of neonates with any of the composite component, neonates with any of the composite component w/o RDS, neonates with any of the composite component w/o RDS and mortality, and individual composite component, RR and 95% CIs, OR and 95% CIs, and p-values will be provided. 	
Sensitivity and Support Statistical Analysis	

 For length of stay, data will be analyzed in a similar fashion as described in Section 7.1.2. 	

Key Secondary Efficacy Statistical Analysis

- Treatment effects within defined subgroups in Section 5.1 will be explored.

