8.1.3. Planned Other Secondary Efficacy Statistical Analyses

Other Secondary Efficacy Statistical Analysis
Endpoint

 • Proportion of neonates with any of the composite neonatal morbidity and mortality excluding RDS • Proportion of neonates with each individual component of the composite neonatal morbidity and mortality endpoints listed in Section 11.5.4. • Neonatal admission to a specialized care unit and length of stay – confirm admission to neonatal intensive or specialized care unit from the medical records • Newborn hospital readmission and length of stay – confirm any neonatal hospital readmission following the birth hospitalization, the reason for admission, and the length of stay from the medical records • Ambulatory surgery – confirm any neonatal ambulatory surgery and the indication for surgery from the medical records • Proportion of births prior to 28^{0/7} weeks' gestation • Proportion of births prior to 32^{0/7} weeks' gestation • Proportion of births prior to 35^{0/7} weeks' gestation • Proportion of births ≤7 days from the first study treatment • Proportion of births ≤48 hours from the first study treatment • Proportion of births ≤24 hours from the first study treatment
Model Specification

 • Binary endpoints will be analyzed in a similar fashion to the neonatal composite analysis in Section 8.1.2. • Neonatal admission to a specialized care unit and length of stay, and ambulatory surgery will be explored in the integrated analysis separately.
Model Results Presentation

 • Data will be analyzed in a similar fashion as described in Section 8.1.2. • Treatment effects within defined subgroups in Section 5.1 will be explored.

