 - Grade 3 or 4 (severe IVH)

OR

- Any grade of IVH with posthemorrhagic hydrocephalus requiring a shunt
- White matter injury, documented on cranial ultrasound or magnetic resonance imaging, as indicated by the following:
 - Multiple cystic lucencies in periventricular white matter (may be bilateral or unilateral, may vary in size, and be diffuse or focal in distribution)

OR

- Porencephalic cyst (not including subependymal or choroid plexus cysts)

OR

- Persistent ventriculomegaly, moderate to severe
- Cerebellar hemorrhage (unilateral or bilateral)

Individual Neonatal Composite Endpoint

- This will be derived for all the conditions included under the composite endpoint. For each individual condition, the variable will be 1 if the condition is satisfied, otherwise, 0.

Neonatal Composite Endpoint without RDS

- Same as the composite endpoint without the RDS condition.

Neonatal Composite Endpoint without RDS and mortality

- Same as the composite endpoint without the RDS and fetal/neonatal death conditions.

Modified Neonatal Composite Endpoint

- Same as the composite endpoint and include the all reported neonatal events. For example, a subject is considered as experience a RDS even without record of CPAP, ventilation or Surfactant. .

Calculation of Gestational Age at Birth and Proportion of Pre-term Births

- Gestational age at birth (weeks) is defined as the gestational age when the baby is born and is captured in the eCRF. If the data are missing, the GA at birth can be calculated as follows:

$$\text{GA at Birth (weeks)} = (\text{GA at Randomization} \times 7 + \text{Time to delivery}) / 7$$

GA at randomization will be converted to 1 decimal place (i.e. 30.2 weeks GA at randomization) prior the calculation.

- Proportion of births prior to $37^{0/7}$, $35^{0/7}$, $32^{0/7}$, or $28^{0/7}$ week's gestation (preterm)

Subjects are considered to have delivered prior to $37^{0/7}$ weeks if the gestational age at birth is less than $37^{0/7}$ weeks (e.g.: < 37.0 weeks). Other proportions also will be calculated in a similar fashion. For proportion of births prior to $32^{0/7}$ and $28^{0/7}$ week's gestation, only mothers who were randomized prior to $32^{0/7}$ and $28^{0/7}$ week's gestation will be included respectively.

- Proportion of births at term ($\geq 37^{0/7}$ week's gestation)

Subjects are considered to have delivered at term if the gestational age is $\geq 37^{0/7}$ (e.g., ≥ 37.0 weeks)

Calculation of Neonatal Hospital Admission

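### The SAP has no sparse-data rule for births before 28 weeks, or for single composite components if they are modelled, under ordinary logistic regression

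*SAP*

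**What the plan says.** SAP 8.1.3 lists each single component of the neonatal composite and births before 28 weeks among the other secondary endpoints. Its model instruction is "Binary endpoints will be analyzed in a similar fashion to the neonatal composite analysis in Section 8.1.2". Section 8.1.2 defines that model as a logit-link regression: "The model will include terms for treatment group, established progesterone use, and GA at randomization". Treatment interactions with GA and progesterone use are also investigated, and kept if significant at the 0.1 level. The only fitting code, in SAP 11.7.2, is a plain PROC LOGISTIC call with neither a Firth option nor an exact statement.

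For births before 28 weeks, SAP 11.5.4 includes "only mothers who were randomized prior to" that gestation. Table 4 in SAP 8.1.1 marks this endpoint for formal statistical analysis.

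For single components the SAP points two ways. Section 8.1.2 promises, for the composite variants "and individual composite component, RR and 95% CIs, OR and 95% CIs, and p-values will be provided". The Table 4 row "Individual neonatal composite endpoint" has no mark under statistical analysis, only under summary table and listing.

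Appendix 9 covers model checking for time to delivery and length of stay only. Section 9 lists what is dropped after early termination; modelling of these endpoints is not on the list. Length of stay has a fallback (the Wilcoxon test). Binary endpoints have none.

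**The concern.** When one arm has no events, or all events, the maximum-likelihood treatment odds ratio is zero, infinite or undefined. The Wald interval and p-value printed beside it then mean nothing. A relative risk derived from that odds ratio, as Protocol 8.3.5.1.2 intends, fails with it. The same happens to the progesterone coefficient when users are few and all share one outcome, and that term cannot be fitted at all if the subset contains no user.

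If the composite's imputation method is carried over as well, the failure spreads. SAP 11.7.2 recovers each standard error from the Wald limits and pools it by Rubin's rules.

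Without a written rule, the method would be chosen after separation warnings appear in unblinded data, although SAP Section 9 says that planned analyses will not change once the blind is broken.

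**Working it through.** **The plan's own figure.** The planned GA shares (Protocol 8.2.1) "will be 7%, 13%, 27%, and 53% (1:2:4:8 ratio), respectively". From the ratio: 1/15 = 6.7%, 2/15 = 13.3%, 4/15 = 26.7%, 8/15 = 53.3%. These round to the stated values.

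**Size of the subset.** SAP 2.3: "A total of 97 patients were blindly randomly assigned to retosiban or atosiban in a 1:1 ratio". Randomised before 28 weeks: 7% + 13% = 20%, and 97 × 0.20 = 19.4. That is about 19 women, or 9 to 10 per arm, since "Subjects within each stratum will be randomly assigned in 1:1 ratio to receive either retosiban or atosiban using an IVRS". The actual number is not stated, and the ITT population includes only dosed women.

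**Births before 28 weeks, 19 women.** The documents give neither this event rate nor the share on progesterone, so both are assumed.
- Share delivering within 3 weeks: 55% (the protocol's planning value for atosiban), 45% or 35%, applied to both arms. Delivery within those weeks was either spread evenly or concentrated early. The implied rate of birth before 28 weeks is about 18–39%, or 19 × 0.18 = 3.4 to 19 × 0.39 = 7.4 expected events for a four-parameter model.
- Progesterone use: 10%, 20% or 30%.
- 500 simulated datasets per setting, main effects only, each tested for complete or quasi-complete separation.

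| Delivering within 3 weeks | Any coefficient not finite | Treatment odds ratio not finite |
|---|---|---|
| 55% | 16–57% | 5–12% |
| 45% | 25–64% | 8–22% |
| 35% | 35–71% | 16–33% |

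Most failures are in the progesterone term. At 10% use, the chance that 19 women include no user is 0.9^19 = 13.5%.

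**Single components, 97 infants (48 and 49 per arm), if modelled.** With incidence p equal in both arms, P(no events in at least one arm) = (1−p)^48 + (1−p)^49 − (1−p)^97. At 1%: 0.617 + 0.611 − 0.377 = 0.851. The last column is simulated, with 10–30% progesterone use.

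| Assumed incidence | An arm with no events | Any coefficient not finite |
|---|---|---|
| 1% | 85% | 92–96% |
| 2% | 61% | 77–91% |
| 3% | 40% | 60–80% |
| 5% | 16% | 33–61% |
| 10% | 1% | 8–38% |

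**Does Firth repair it?** With a single-level progesterone term dropped, Firth's penalised likelihood had a finite maximum in all 200 simulated 19-woman subsets per setting. It also converged in every simulated dataset of 97. Precision stays poor. In the subset the median standard error of the treatment log odds ratio was about 1.09 to 1.38, so the 95% limits are the odds ratio multiplied and divided by exp(1.96 × 1.09) ≈ 8.5 to exp(1.96 × 1.38) ≈ 15. For a 2% component in 97 infants the factor is also about 15. In one subset the penalised treatment log odds ratio was still 12.7, so a finite estimate is not always a usable one.

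**The case against.** Four points weigh against a stronger reading.

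- A reader might take the 16–71% as the failure rate of the treatment comparison. It is not. Progesterone use is a nuisance covariate, and if only its coefficient diverges the treatment odds ratio can still be finite. At the protocol's own 55%, the treatment odds ratio fails in 5–12% of datasets. This stands.
- A reader might infer that the SAP commits to modelling every component. Table 4 shows summaries only. SAP Appendix 11 says that only its listed displays will be produced, and it lists no separate table for individual components. Sections 8.1.2 and 8.1.3 say otherwise, so what is established is an inconsistency. This stands.
- Component incidences and progesterone use appear nowhere in the documents. At 10% incidence the treatment odds ratio almost always exists. This stands, and it is why ranges are shown. Strict definitions (severe haemorrhage, advanced or treated retinopathy, culture-positive meningitis) and a planned 53% of women entering at 31 weeks or later make low counts plausible for some components, but they do not prove it.
- The stakes are low. These are other secondary endpoints in a terminated trial without multiplicity adjustment, and counts by arm are promised anyway, so an empty cell would be visible. This limits the importance of the point but does not supply the missing rule.

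**Conclusion.** The point holds in a limited form. Ordinary logistic regression with two covariates is the written method, and no fallback is given. For births before 28 weeks, formal analysis is clearly planned in a subset of about 19 women if the planned GA mix held. There the full set of estimates fails in about 16–71% of datasets and the treatment odds ratio in about 5–33%, given event rates of about 18–39%, progesterone use of 10–30% and no treatment effect.

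For single components the SAP must first settle whether they are modelled. If they are, an arm without events is likely at 1–2% incidence (85% and 61%), common at 3% (40%), less so at 5% (16%) and rare at 10% (1%). The documents do not support saying that the treatment odds ratios will generally fail to exist. This is a minor amendment that is worth making before unblinding.

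**What to change.** 1. Reconcile Table 4 with SAP 8.1.2 and 8.1.3 on single components. Either present counts and percentages only, or model them under the rule below.
2. For births before 28 weeks, and for components if modelled, pre-specify Firth penalised logistic regression. Use main effects only and drop any covariate that has a single level in the analysed subset. Below a pre-set minimum number of events, report counts only.
3. Where nothing is imputed, report profile-likelihood confidence intervals.
4. Where multiple imputation is used, pool the Firth log odds ratio and its own standard error directly. The code in SAP 11.7.2 divides the distance between the log limits by 2 × 1.96, which assumes symmetric limits; profile limits are generally not symmetric. The logistic imputation step needs its own guard against separation.

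The cost is a few sentences, one option in the fitting procedure and a small change to the pooling code. The drawbacks are some shrinkage of the odds ratio, with a penalty that largely determines the estimate when a cell is empty, and intervals that remain very wide (odds ratio multiplied and divided by about 8.5 to 15). Counts alone are therefore a reasonable choice for the sparsest outcomes.

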8.2. Safety Analyses

All safety summaries will be performed for the Safety Population as defined in Section 4 of this document. A listing of all safety data will be presented.

8.2.1. Overview of Planned Analyses

The safety analyses will be based on the Maternal and Neonatal Safety Populations, unless otherwise specified.

Table 5 provides an overview of the planned analyses with further details of data displays being presented in Appendix 11: List of Data Displays.

Table 5 Overview of Planned Safety Analyses

Endpoints	Observed				Change from Baseline			
	Summary		Individual		Summary		Individual	
	T	F	F	L	T	F	F	L
Exposure								
Extent of Exposure	Y				Y			
Maternal Endpoints								
Adverse Events								
All AEs	Y				Y			
AEs by Maximum Grade or Intensity	Y				Y			
Most Common AEs	Y				Y			
Serious AEs	Y				Y			
AEs of special interest	Y				Y			
Disease-related AEs	Y				Y			
AEs leading to Deaths					Y			
Clinical Laboratory	Y				Y	Y		Y
Maternal Vital Signs	Y				Y	Y		Y
Maternal Health Care Resource Use	Y				Y			
Fetal Endpoints								
Adverse Events								
All AEs	Y				Y			
AEs by Maximum Grade or Intensity	Y				Y			
Most Common AEs	Y				Y			
Serious AEs	Y				Y			
AEs of special interest	Y				Y			
Fetal Heart Rate	Y				Y	Y		Y
Neonatal Endpoints								
Adverse Events								
All AEs	Y				Y			
AEs by Maximum Grade or Intensity	Y				Y			
Most Common AEs	Y				Y			
Serious AEs	Y				Y			
AEs of special interest	Y				Y			
Disease-related AEs	Y				Y			
Neonatal Health Care Resource Use	Y				Y			
Neonatal Birth Record	Y				Y			

Endpoints	Observed				Change from Baseline			
	Summary		Individual		Summary		Individual	
	T	F	F	L	T	F	F	L
APGAR scores	Y			Y				
Any Complications				Y				

NOTES :

- T = Table, F = Figure, L = Listing, Y = Yes display generated.
- Stats Analysis = Represents TFL related to any formal statistical analyses (i.e. modelling) conducted.
- Summary = Represents TFL related to any summaries (i.e. descriptive statistics) of the observed raw data.
- Individual = Represents FL related to any displays of individual subject observed raw data.

